5.4.1.1 Use of DataCore/Epic Information for Recruitment Purposes

This study will utilize EPIC to identify subjects. The PI and Research Coordinator will have access to the EPIC search results.

Any recruitment information sent by email will utilize Send Safe email.

Once potential subjects have been identified, the study team will notify the treating physician (TP) that they have patients eligible to participate as follow:

• TP has been notified that the study team will contact potential subjects directly, by letter, phone, email, or the MyChart portal etc.

Once contact is made, approved recruitment language will be used to communicate the reason they are being contacted and subjects will be asked if they are interested in participating in this specific study. Should the potential subjects agree, the study team will provide the subjects with information regarding the next steps for participation.

If a subject requests information regarding opting out of further recruitment for all research, subjects will be directed to contact [contact] or [name].

5.5 Duration of Study Participation

The study will last about 4 months and will involve about 17 visits. This includes the consenting process, screening procedures and all study visits.

5.6 Total Number of Participants and Sites

Recruitment will end when approximately 50 participants are enrolled. It is expected that approximately 50 participants will be enrolled in order to produce 30 evaluable participants. These participants between the ages of 18 and 75 are to be entered into this study at NYU Langone Medical Center. This research project will only be taking place at this site. This study will be an out-patient study. The study visits will be at the NYU Langone Preston Robert Tisch Center for Men's Health, [name].

5.7 Participant Withdrawal or Termination

5.7.1.1 Reasons for Withdrawal or Termination

Participants are free to withdraw from participation in the study at any time upon request. An investigator may terminate participation in the study if:

- Any clinical adverse event (AE) or other medical condition or situation occurs such that continued participation in the study would not be in the best interest of the participant
- The participant meets an exclusion criterion (either newly developed or not previously recognized) that precludes further study participation
- At any point during the study, a subject is found to have abnormal urine sodium or osmolality levels or an abnormal comprehensive metabolic panel
- They experience a significant rise in blood pressure (>150/100) or intolerable side effects (nausea, vomiting, headache, or significant worsening of tinnitus)

5.7.2 Handling of Participant Withdrawals or Termination

Subjects may withdraw from the study at any time. Subjects that choose to withdraw early from the study will be voluntarily surveyed for reasons for withdrawal. They will be asked for permission to continue to utilize the data collected up to the point of withdrawal for research purposes. Should they decline, all data past the note of withdrawal will be deleted from the record system. Subjects will be required to return any unused samples of nasal spray.

We will reach out to those withdrawn or terminated participants or those who discontinue the study agent but remain in the study for follow-up via 3 phone calls to them. Should participants not respond to our phone calls, a certified letter will be sent to their home address. For those participants who withdrew because of AEs, we will try to continuously follow them until AEs resolve.

We plan to replace participants who withdraw or discontinue the study early, in order to collect the minimum data required to determine the efficacy of the study drug, per Section 9.3 of the Statistical Considerations for the study, Analysis Datasets.

5.8 Premature Termination or Suspension of Study

This study may be temporarily suspended or prematurely terminated if there is sufficient reasonable cause. Written notification, documenting the reason for study suspension or termination, will be provided by the investigator to the IRB. If the study is prematurely terminated or suspended, the PI will promptly inform the IRB and will provide the reason(s) for the termination or suspension.

Circumstances that may warrant termination or suspension include, but are not limited to:

- Determination of unexpected, significant, or unacceptable risk to participants
- Demonstration of efficacy that would warrant stopping
- Insufficient compliance to protocol requirements
- Data that are not sufficiently complete and/or evaluable
- Determination of futility

Study may resume once concerns about safety, protocol compliance, data quality are addressed and satisfy the IRB.

6 Study Agent

6.1 Study Agent(s) and Control Description

The investigational product, oxytocin nasal spray (45 units/0.1mL for 100mL) is composed of: oxytocin 10 unit/MG/mannitol trituration (4.500g), magnesium chloride crystals (6.080g), citric acid anhydrous gran. (0.284g), sodium citrate powder (5.660g), sterile water for irrigation (100.000mL), and Pcca Mucolox liquid base(10.000mL).

See Oxytocin Nasal Spray package insert (29).

The placebo nasal spray consists of: magnesium chloride crystals (6.080g), citric acid anhydrous gran. (0.284g), sodium citrate powder (5.660g), sterile water for irrigation (100.000mL), and Pcca Mucolox liquid base (10.000mL). Both placebo and active drug will be handled and stored the same way.

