Brief Summary	The purpose of this study is to evaluate the effects of high-dose intranasal oxytocin for treating tinnitus. The hypothesis is that high dose intranasal oxytocin can significantly reduce tinnitus severity and disability.
Methodology	Pilot, proof of concept, randomized, placebo-control, parallel study
Endpoint	The primary efficacy endpoint is the area under the VAS curve from baseline for all randomized participants during the blinded study phase. The secondary endpoint, which is exploratory, will be improvement ($p < 0.10$) in the Tinnitus Handicap Inventory Severity Scale (THI)/Clinical Global Impression Scale (CGI) and Tinnitus Functional Index (TFI).
Study Duration	Time from when the study opens to enrollment until completion of data analysis will be approximately 1 year.
Participant Duration	Participant participation will last approximately 4 months and involve about 17 visits.
Duration of IP administration	Investigational product administration will last 15 weeks. The first 9 weeks of this period will involve the administration of active study medication to all participants. During the last 6 weeks, participants will be randomized to receive either placebo or active study medication for the remainder of the study.
Population	We will recruit patients from NYU Langone Medical Center's Departments of Otolaryngology and Neurology. Eligible individuals will be age 18 to 75 with continuous perception of tinnitus for > 6 months, with a normal ENT evaluation within the past year.
Study Sites	NYU Langone Medical Center
Number of participants	50 participants expected to be enrolled with a goal of 30 study participants remaining after accounting for screen failures and participants who withdrew from the study.
Description of Study Agent/Procedure	The investigational product, oxytocin nasal spray (45 units/0.1mL for 100mL) is composed of: oxytocin 10 unit/MG/mannitol trituration (4.500g), magnesium chloride crystals (6.080g), citric acid anhydrous gran. (0.284g), sodium citrate powder (5.660g), sterile water for irrigation (100.000mL), and Pcca Mucolox liquid base (10.000mL). The dose for the oxytocin nasal spray will range from 30 to 45 IU per puff to be administered four times per day, for an equivalent to 120 to 180 IU oxytocin/day.

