6.1.2 Formulation, Appearance, Packaging, and Labeling

This nasal spray will be a liquid prepared at VLS Pharmacy/New Drug Loft and contained in 30mL amber glass bottles with nasal sprayers. Both active drug and the placebo will appear identical in the glass bottles. These bottles will be labeled with subject specific labels to be marked by the study coordinator. The label will also say "Oxytocin/Placebo." This study medication is investigational and will be formulated specifically for the purpose of meeting the trial plan.

6.1.3 **Product Storage and Stability**

Study agent and placebo will be stored in amber glass bottles in a secure refrigerator that only study personnel will have access to. The medications will be kept between 36°F to 46°F (2°C - 8°C). They cannot be frozen or exposed to direct light. After its preparation, the study agent is good for 30 days in the refrigerator. It must be kept out of the reach of children.

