6.1.5 Dosing and Administration

After the baseline period of the study (1 week), subjects will receive intranasal oxytocin for 9 weeks. They will receive a spray bottle with study medication at Visit 3 to be self-administered at home four times per day (9AM, 1PM, 5PM, and 9PM). They will be instructed to apply 1 puff (the equivalent of 30 to 45 oxytocin IU) in one nostril four times per day, equivalent to 120 to 180 IU per day.

Subjects will be shown the proper way to use the nasal spray and administer the study medication. With their head facing forward, not tilted up or down, they should place the sprayer in one nostril and spray once while holding their breath. They should then pinch both nostrils closed for 5 seconds. They will be instructed not to sniff in or blow their nose for at least 5 minutes after administration. During the following 6 weeks of the study, subjects may receive placebo or oxytocin nasal spray. The placebo will be administered in the same manner as the active study drug, with 1 puff in one nostril four times per day (9AM, 1PM, 5PM, and 9PM). If the subject is randomized to the active drug during this phase, their dose will be the same dose they received during Week 9 of the study, during the non-blinded phase.

The nasal spray should be refrigerated when not being used. Subjects will also have a re-freezable bag to store their spray bottles in when not near a refrigerator.

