6.1.7 Starting Dose and Dose Escalation Schedule

All subjects will begin at a dose of 30 IU 4 times daily for 2 weeks. If no response is reported (defined as a decrease in VAS of < 2), they will have the dose increase by 5 IU per spray every 2 weeks, until a maximum dose of 45 IU 4 times daily. If patients report improvement (defined as improvement in VAS >3) at any dose, they will remain at that dose through the end of the second phase. In the event that the patient experiences a moderate side effect, the dose will be decreased to the previous dose for the remainder of this phase.

Subjects will be informed that depending on their responses, their dose may stay the same, be increased or decreased. Accordingly, after Visit 3, active drug will be dispensed at office study visits every 2 weeks during the non-blinded phase.

The dose for the oxytocin nasal spray will be 30, 35, 40, or 45 IU per puff to be administered four times per day. This dosage was determined by treating 2 patients (as described above) with tinnitus in our clinical practice. Both patients were initially treated with 16 IU oxytocin nasal spray daily as detailed in the Azevedo et al study (5). Both patients noted slight improvement, and over the course of several months the dose was gradually increased while following their clinical course and vital signs and laboratory studies. Maximum benefit was noted at a dose of 45 IU QID.

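### One listed strength (45 units/0.1 mL) and one puff per dose cannot account for four per-puff dose levels, and the final batch volume is not stated

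*Combined protocol and SAP*

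**What the plan says.** The Protocol Summary and section 6.1 give the same single active composition. Section 6.1 reads "The investigational product, oxytocin nasal spray (45 units/0.1mL for 100mL) is composed of: oxytocin 10 unit/MG/mannitol trituration (4.500g", and its ingredient list goes on to include "sterile water for irrigation (100.000mL), and Pcca Mucolox liquid base(10.000mL".

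Section 6.1.5 sets the administration: "They will be instructed to apply 1 puff (the equivalent of 30 to 45 oxytocin IU) in one nostril four times per day". Section 6.1.7 sets the levels: "The dose for the oxytocin nasal spray will be 30, 35, 40, or 45 IU per puff". Everyone starts at the lowest level. Changes are in 5 IU steps per spray, depending on response, and section 6.1.8 adds a step down for moderate side effects. Under section 6.1.5, a participant randomized to active drug keeps the Week 9 dose through the blinded phase.

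On packaging, section 6.1.2 says that the product comes in 30 mL bottles with nasal sprayers: "These bottles will be labeled with subject specific labels to be marked by the study coordinator". The label also carries a common oxytocin/placebo wording, and no strength is mentioned. Section 6.2 calls for a log of drug assigned, consumed and remaining, again without mention of strength.

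**The concern.** With one concentration and one puff per dose, the content of a puff can change only if the volume per puff changes. Sections 6.1 to 6.2 describe no variable-volume sprayer, second strength or second puff count. Taken literally, the product in section 6.1 and the escalation in section 6.1.7 do not fit together. The Protocol Summary contains the conflict within one entry: it lists one strength and then a range of IU per puff.

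Several parts of the plan depend on the delivered dose:
- the starting level and the two-weekly escalation;
- the reduction for side effects;
- the Week 9 dose carried into the blinded phase;
- the descriptive summary by dosage group, with its effect size, in sections 4.2.1.2 and 9.4.7.6.

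If the nominal level does not determine what is in the puff, the dosage groups do not separate doses, and tolerability at a level cannot be attributed to that level. Section 2.4.1.1 links high dose to changes in sodium and osmolality, so the delivered dose matters for reading the safety data too.

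The ingredient list raises a second, smaller question. It gives 100 mL of water and 10 mL of liquid base for a batch labelled as 100 mL.

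**Working it through.** **Inputs.** From section 6.1: 4.500 g of trituration at 10 units/mg; labelled strength 45 units/0.1 mL in a 100 mL batch; water 100 mL; liquid base 10 mL. From section 6.1.5: one puff per administration, four times daily. From section 6.1.7: levels of 30, 35, 40 and 45 IU per puff. Volume per puff: not stated anywhere, so treated as an assumption with a range.

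**1. Reproduce the stated strength.** 4,500 mg × 10 units/mg = 45,000 units. 45,000 / 100 mL = 450 units/mL = 45.0 units/0.1 mL. The label reproduces exactly at a final volume of 100 mL.

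**2. Puff volume that each level would need at that strength** (dose / 450 units/mL), and what a fixed 0.1 mL puff would give instead:

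| Nominal level (IU) | Volume needed (mL) | Given by a 0.1 mL puff (IU) | Difference | Daily: nominal vs given (IU) |
|---|---|---|---|---|
| 30 | 0.0667 | 45 | 45/30 − 1 = +50% | 120 vs 180 |
| 35 | 0.0778 | 45 | 45/35 − 1 = +29% | 140 vs 180 |
| 40 | 0.0889 | 45 | 45/40 − 1 = +12.5% | 160 vs 180 |
| 45 | 0.1000 | 45 | 0 | 180 vs 180 |

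The four levels need four different volumes, so no single volume serves them all.

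**3. Sensitivity to the unstated puff volume** (450 units/mL × volume). The 0.1 mL figure is inferred from the way the strength is expressed and from the 45 IU maximum. Other assumed volumes give:
- 0.05 mL: 22.5 IU
- 0.07 mL: 31.5 IU
- 0.10 mL: 45 IU
- 0.14 mL: 63 IU

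In every case the result is one dose. The percentages in step 2 apply only at 0.1 mL. The conclusion that one strength and one fixed volume give one dose does not depend on the volume.

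**4. Final batch volume.** Listed liquids: 100 + 10 = 110 mL. If they are simply added, 45,000 / 110 = 409.1 units/mL = 40.9 units/0.1 mL, and 40.9/45 − 1 = −9.1%. In a 0.1 mL puff the shortfall is 45 − 40.9 = 4.1 IU, or 4.1/5 = 82% of one escalation step. If instead the batch is made up to 100 mL, step 1 applies and there is no discrepancy. The text does not say which. Any further volume from the dissolved solids is not calculated, because the documents give no basis for it.

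**The case against.** The strongest reply is that several strengths are made and that section 6.1 shows only one of them. Three features of the text fit this. Section 6.1.7 expresses the levels per puff and the steps per spray, and section 6.1.5 equates one puff with a range, so the content of a puff is evidently meant to vary. Section 6.1.7 ties two-weekly dispensing to possible dose changes, which would allow a bottle of another strength to be issued. Section 6.1.2 says that the product will be made up to suit the trial plan. Nowhere is 45 units/0.1 mL called the only strength.

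This reply stands as far as it goes. A reader might infer that the lower levels cannot be delivered, or that participants assigned 30 IU received 45 IU. The documents show neither. The first inference ignores the compatible wording, and the second also needs an unstated puff volume and a pharmacy that ignored section 6.1.7. What the reply does not do is supply the specification. If there are several strengths, up to three of the four active products are missing from the protocol.

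A reader might also infer that the ingredient list contradicts its own strength. It does not: the strength is exact at the labelled 100 mL.

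On labelling, section 6.1.2 does not claim to list everything on the label, and its statement about identical appearance concerns active versus placebo. So the text does not show that strengths would be indistinguishable, only that no means of telling them apart is described.

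Section 6.1 also refers to a package insert, which was not available for this check. By the reference list it comes from a different compounding pharmacy than the supplier named in section 6.1.1, and section 4.1 mentions a change of pharmacy, so it cannot be assumed to fill the gap.

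Finally, the primary comparison is active versus placebo, and the dosage-group summary is descriptive. The gap does not undermine the randomized contrast itself. It leaves unclear what dose that contrast describes.

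**Conclusion.** The intervention specification is inconsistent as written. One listed strength with one puff of fixed volume can give at most one of the four required levels, and the means of delivering the others is not described. This part rests only on the puff volume being fixed, since no adjustable device is mentioned.

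The size of any discrepancy between nominal and delivered dose cannot be determined from the documents. It would be +50%, +29% and +12.5% at 30, 35 and 40 IU if the listed strength were used throughout with an assumed 0.1 mL puff. It would be nil if a suitable strength were made for each level.

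The batch volume is an ambiguity and not an arithmetic error: 45.0 units/0.1 mL at a final 100 mL, or 40.9 (−9.1%) if the listed liquids are simply added. No view is taken on which dose, strength or puff rule is right.

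**What to change.** Reconcile the Protocol Summary and sections 6.1, 6.1.2, 6.1.5 and 6.1.7 so that they agree on three items: the strength or strengths of active product, the volume per actuation, and the final batch volume. For the last, one clause saying whether the listed water is added in full or used to make up to volume is enough.

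Record the strength dispensed to each participant in the section 6.2 accountability log. In the blinded phase use a code carried by both arms, so that the entry does not reveal allocation. The delivered dose can then be verified for the titration and for the dosage-group summary in sections 4.2.1.2 and 9.4.7.6.

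The cost is a protocol amendment, a check against the pharmacy's compounding records and one extra log entry per bottle. No additional participants are needed. For anyone already treated, the pharmacy would have to confirm which strengths were supplied.

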6.1.1 Acquisition

The study agent and placebo will be prepared and acquired from VLS Pharmacy/New Drug Loft. They will be shipped to the study site at the Center for Men's Health, [name].

6.1.2 Formulation, Appearance, Packaging, and Labeling

This nasal spray will be a liquid prepared at VLS Pharmacy/New Drug Loft and contained in 30mL amber glass bottles with nasal sprayers. Both active drug and the placebo will appear identical in the glass bottles. These bottles will be labeled with subject specific labels to be marked by the study coordinator. The label will also say "Oxytocin/Placebo." This study medication is investigational and will be formulated specifically for the purpose of meeting the trial plan.

6.1.3 **Product Storage and Stability**

Study agent and placebo will be stored in amber glass bottles in a secure refrigerator that only study personnel will have access to. The medications will be kept between 36°F to 46°F (2°C - 8°C). They cannot be frozen or exposed to direct light. After its preparation, the study agent is good for 30 days in the refrigerator. It must be kept out of the reach of children.

6.1.4 Preparation

The study drug and placebo nasal sprays will be mixed/prepared by VLS Pharmacy/New Drug Loft and shipped to the study site. They can be contacted at [name].

6.1.5 Dosing and Administration

After the baseline period of the study (1 week), subjects will receive intranasal oxytocin for 9 weeks. They will receive a spray bottle with study medication at Visit 3 to be self-administered at home four times per day (9AM, 1PM, 5PM, and 9PM). They will be instructed to apply 1 puff (the equivalent of 30 to 45 oxytocin IU) in one nostril four times per day, equivalent to 120 to 180 IU per day.

Subjects will be shown the proper way to use the nasal spray and administer the study medication. With their head facing forward, not tilted up or down, they should place the sprayer in one nostril and spray once while holding their breath. They should then pinch both nostrils closed for 5 seconds. They will be instructed not to sniff in or blow their nose for at least 5 minutes after administration. During the following 6 weeks of the study, subjects may receive placebo or oxytocin nasal spray. The placebo will be administered in the same manner as the active study drug, with 1 puff in one nostril four times per day (9AM, 1PM, 5PM, and 9PM). If the subject is randomized to the active drug during this phase, their dose will be the same dose they received during Week 9 of the study, during the non-blinded phase.

The nasal spray should be refrigerated when not being used. Subjects will also have a re-freezable bag to store their spray bottles in when not near a refrigerator.

6.1.6 Route of Administration

The route of administration for the study medication is intranasally.

6.1.7 Starting Dose and Dose Escalation Schedule

All subjects will begin at a dose of 30 IU 4 times daily for 2 weeks. If no response is reported (defined as a decrease in VAS of < 2), they will have the dose increase by 5 IU per spray every 2 weeks, until a maximum dose of 45 IU 4 times daily. If patients report improvement (defined as improvement in VAS >3) at any dose, they will remain at that dose through the end of the second phase. In the event that the patient experiences a moderate side effect, the dose will be decreased to the previous dose for the remainder of this phase.

Subjects will be informed that depending on their responses, their dose may stay the same, be increased or decreased. Accordingly, after Visit 3, active drug will be dispensed at office study visits every 2 weeks during the non-blinded phase.

The dose for the oxytocin nasal spray will be 30, 35, 40, or 45 IU per puff to be administered four times per day. This dosage was determined by treating 2 patients (as described above) with tinnitus in our clinical practice. Both patients were initially treated with 16 IU oxytocin nasal spray daily as detailed in the Azevedo et al study (5). Both patients noted slight improvement, and over the course of several months the dose was gradually increased while following their clinical course and vital signs and laboratory studies. Maximum benefit was noted at a dose of 45 IU QID.

